#### **4.6.8 Gastrointestinal adverse events**

In the ALTER0303 clinical study, diarrhea was the most frequently reported treatment-related gastrointestinal AE. Diarrhea was reported by 86 patients (29.25%) in the anlotinib group, including 3 patients (1.02%) with grade 3 diarrhea. Other gastrointestinal AEs included oropharyngeal pain, stomatitis, vomiting, nausea, and abdominal pain. Supportive care for gastrointestinal AEs requiring treatment may include oral care, antiemetic and antidiarrheal treatments.

Supportive treatments may be given for patients experiencing grade 1–2 diarrhea throughout study, such as symptomatic treatment (e.g., 4 mg oral loperamide, then 2 mg every 2 hours until diarrhea resolves) at the time of onset. If grade 3/4 diarrhea is observed, anlotinib should be interrupted. If grade 3/4 diarrhea is observed again after anlotinib resumption, treatment should be continued at a lower dose. If the adverse reaction persists, discontinuation is recommended.

#### **4.6.9 Hyperlipidaemia**

The ALTER0303 study showed that anlotinib resulted in increased triglycerides and cholesterol. Hence, patients with hyperlipidemia are recommended to change to a low-fat diet. Hypercholesterolemia ( $27.75$  mmol/L) or hypertriglyceridemia ( $\geq 2.5\times$  ULN) of grade 2 or higher should be treated with hydroxymethylglutaryl coenzyme A (HMG-CoA) reductase inhibitors (e.g., atorvastatin) or appropriate lipid-lowering drugs.

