### 4.4 Dose Adjustment

Adverse reactions should be closely monitored during the administration of the study drug, and the dose should be adjusted according to the patient's tolerance. Adverse reactions caused by the study drug can be treated by symptomatic treatment, drug interruption and/or dose adjustment. The dose should be adjusted under the guidance of a physician according to the severity of adverse reactions: 1) First dose adjustment: 10 mg qd for 2 weeks, followed by 1-week discontinuation; 2) Second dose adjustment: 8 mg qd for 2 weeks, followed by 1-week discontinuation. If the dose of 8 mg remains intolerable, the drug should be permanently discontinued.

Dose adjustments for each adverse reaction are as follows:

- **Hematologic Toxicities**

(1) Platelet count decreased

Grade of AE	Treatment Recommendations	Dose Adjustment
Grade 1	Perform visits as scheduled	Maintain the original dose

Grade 2	Delay dosing until AE resolves to $\leq$ grade 1	Maintain the original dose
Grade 3	Delay dosing and provide medical interventions until AE resolves to $\leq$ grade 1	Continue at a lower dose
Grade 4	Permanent discontinuation	/

(2) Neutrophil count decreased

Grade of AE	Treatment Recommendations	Dose Adjustment
Grade 1	Perform visits as scheduled	Maintain the original dose
Grade 2	Delay dosing until AE resolves to $\leq$ grade 1	Maintain the original dose
Grade 3-4	Delay dosing and provide medical interventions until AE resolves to $\leq$ grade 1	Continue at a lower dose

● **Non-Hematologic Toxicities**

(1) Hepatic function abnormal (elevated ALT, AST or TBIL)

Grade of AE	Treatment Recommendations	Dose Adjustment
Grade 1	Perform visits as scheduled	Maintain the original dose
Grade 2	Delay dosing until AE resolves to $\leq$ grade 1	Maintain the original dose
Grade 3-4	Delay dosing and provide medical interventions until AE resolves to $\leq$ grade 1	Continue at a lower dose

(2) Proteinuria

Grade of AE	Definition	Treatment Recommendations	Dose Adjustment
Grade 1	1+ proteinuria, or urine protein $<$ 1.0 g/24 h	Perform visits as scheduled	Maintain the original dose
Grade 2	2+ proteinuria, and urine protein $<$ 1.0 g/24 h	Perform visits as scheduled	Maintain the original dose
	2+ proteinuria, and urine protein is 1.0–3.4 g/24 h	Delay dosing and provide medical interventions until proteinuria $\leq$ 2+ and urine protein $<$ 1.0 g/24 h	Maintain the original dose

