#### **4.6.4 QT interval prolongation**

Anlotinib can prolong the QT/QTc interval, which may increase the risk of ventricular tachyarrhythmias (e.g., torsades de pointes) or sudden death. Therefore, patients with congestive heart failure, electrolyte abnormality, or receiving medications known to prolong the QTc interval should undergo regular (every 3–6 weeks) electrocardiogram and electrolyte (sodium, magnesium, potassium, and calcium) tests. If the results of two consecutive independent ECG show QTc interval  $> 500$  ms, anlotinib should be interrupted until QTc interval is  $\leq 480$  ms or returns to baseline level (if QTc interval at baseline is  $> 480$  ms), then the administration can be continued at a lower dose with close ECG monitoring.

For patients with any grade of QTc prolongation ( $\geq 450$  ms) accompanied by torsades de pointes, polymorphic ventricular tachycardia, symptoms or signs of severe arrhythmia, permanent discontinuation of the study drug and specialized cardiovascular treatment are recommended.

Patients with underlying cardiac dysfunction should undergo echocardiography every 6 weeks, and discontinuation is recommended for patients with a left ventricular ejection fraction  $< 50\%$ .

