#### **4.6.5 Proteinuria and renal function abnormal**

Proteinuria is one of the common adverse reactions of VEGFR inhibitors. Therefore, urinalysis should be performed weekly for patients throughout the treatment. Patients with urine protein  $\geq ++$  for 2 consecutive tests should undergo a 24-hour urine protein test. Measures including treatment interruption, dose adjustment and permanent discontinuation are recommended according to the severity of adverse reactions (Table 1).

Recommended drugs: Compound Nephritis Tablets. ACEIs and ARBs can be provided as they can lower renal tubular pressure and thereby alleviate proteinuria and reduce the risk of potential adverse cardiac events.

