#### **4.6.6 Thyroid insufficiency**

In the ALTER0303 study, hypothyroidism was observed in 58 patients (19.39%) of the anlotinib group, including 1 patient (0.34%) with grade 3 hypothyroidism. Grade 1 hypothyroidism was observed in 4 patients (2.80%) of the placebo group. Thyroid function should be tested prior to the first dose and closely monitored throughout the treatment for all subjects. All subjects receiving anlotinib should be closely monitored for symptoms and signs of decreased thyroid function, including cold intolerance, decreased appetite, and edema. Patients with underlying hypothyroidism or hyperthyroidism should be given appropriate standard treatment when receiving anlotinib. Thyroid function [thyroid stimulating hormone (TSH), triiodothyronine (T3), tetraiodothyronine (T4)] should be tested every 3–6 weeks for patients with symptoms and signs of thyroid insufficiency. When TSH  $\geq$  20 mU/L or T3, T4, FT3 or FT4 is lower than the normal value, symptomatic treatment (e.g., Euthyrox) should be given as soon as possible.

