## **7. SAFETY EVALUATION**

Safety is evaluated as per NCI CTCAE v5.0 (see Attached Appendix III) in this study. The investigator is responsible for monitoring the safety of all subjects enrolled in this study and recording any AEs and serious adverse events (SAEs).

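### Section 4.6.9 ties lipid treatment to a laboratory threshold, but no scheduled chemistry list measures triglycerides or cholesterol (minor; cheap to improve)

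*Protocol*

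**What the plan says.** On the drug effect, section 4.6.9 says: "The ALTER0303 study showed that anlotinib resulted in increased triglycerides and cholesterol". Section 1.5 separately lists raised triglycerides among the main adverse reactions in the phase I study.

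On management, section 4.6.9 has two steps. The first is dietary: "Hence, patients with hyperlipidemia are recommended to change to a low-fat diet". The second is pharmacological and depends on a laboratory grade: hypercholesterolaemia, or hypertriglyceridaemia at 2.5 times the upper limit of normal or more, "of grade 2 or higher should be treated with hydroxymethylglutaryl coenzyme A (HMG-CoA) reductase inhibitors (e.g., atorvastatin) or appropriate lipid-lowering drugs". No frequency of lipid testing is given.

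On monitoring in general, section 4.4 says "Adverse reactions should be closely monitored during the administration of the study drug", and section 7 says "The investigator is responsible for monitoring the safety of all subjects enrolled in this study". Section 5.6 has relevant examinations recorded when an adverse event prompts an unscheduled visit.

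On two other laboratory toxicities, the protocol is explicit. Section 4.6.5 says of proteinuria: "Therefore, urinalysis should be performed weekly for patients throughout the treatment". Section 4.6.6 says: "Thyroid function should be tested prior to the first dose and closely monitored throughout the treatment for all subjects". Both tests also appear in the per-cycle list in 5.3.

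On use of the data, the Synopsis counts laboratory parameters among the safety endpoints, and section 9.3.2 plans to calculate the incidence of adverse events.

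**The concern.** A treatment rule triggered by a laboratory value works only if the value is measured. Here the protocol names the effect, sets the trigger, itemises the blood tests visit by visit, and leaves out the two analytes that the trigger needs. Which analytes are drawn at which visit is a protocol matter, not something usually left to a statistical analysis plan.

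Two things are at stake. The first is patient management: someone who meets the 4.6.9 threshold may be recognised late or not at all. The second is interpretation of the safety data. If lipids are tested only where an investigator thinks to order them, the incidence reported under 9.3.2 partly reflects who was tested. Section 7.1 counts worsening of a pre-existing condition as an adverse event, and sections 7.4 and 9.3.2 ask for a judgement on relationship to the drug. Both are hard to assess without a baseline.

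**Working it through.** There is no planned figure to reproduce. The check is a comparison of sections, followed by a count of what the remedy would require.

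**Step 1: the scheduled panels.** The lists in 5.1, 5.3, 5.4 and 5.5 are identical: ALT, AST, GGT, total bilirubin, direct bilirubin, AKP, urea nitrogen or urea, total protein, albumin, creatinine, glucose, LDH, K, Na, Ca, Mg and Cl. That is 17 analytes. Triglycerides and cholesterol appear in 0 of the 4 lists.

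**Step 2: other places where a lipid test could sit.** Section 5.3 does not hold all the testing. Weekly urinalysis is in 4.6.5 and frequent blood pressure measurement is in 4.6.3, so the toxicity sections must be read as well. Section 4.6.9 gives no interval. The laboratory eligibility criteria in 3.3.9 name no lipid. Section 5.6 records what was examined at adverse-event-driven visits and does not call for a lipid test.

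**Step 3: side by side.**

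| Toxicity | Monitoring in 4.6 | In the per-cycle list (5.3) |
|---|---|---|
| Proteinuria | Weekly urinalysis (4.6.5) | Yes |
| Thyroid | Before first dose and throughout (4.6.6) | Yes |
| Lipids | None stated (4.6.9) | No |

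Lipids are not the only omission. Raised lipase, named in the same phase I sentence in 1.5, is not in the chemistry lists either.

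**Step 4: size of the effect.** The share of elevations missed is 1 minus the share of affected patients who are tested while elevated. The documents give neither that share nor a lipid incidence. The possible range is therefore 0% (every investigator tests under the general duties) to 100% (none does), and no case count can be derived.

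**Step 5: samples needed for the remedy, 39 patients.** Treatment length is an assumption. Six cycles is the median on anlotinib in the phase III lung cancer study described in 1.5; 2 and 12 cycles are illustrative.

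Tested before each cycle, a patient with n cycles has 1 screening sample, (n − 1) pre-cycle samples, 1 at early termination and 1 at day 30, which is n + 2:

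- n = 2: 4 × 39 = 156
- n = 6: 8 × 39 = 312
- n = 12: 14 × 39 = 546

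Tested every two cycles (before cycles 3, 5 and so on):

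- n = 2: (1 + 0 + 1 + 1) × 39 = 117
- n = 6: (1 + 2 + 1 + 1) × 39 = 195
- n = 12: (1 + 5 + 1 + 1) × 39 = 312

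These are upper counts for each scenario, because 5.5 asks for early-termination tests only when none were done in the 7 days before withdrawal.

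**The case against.** The strongest reply is that nothing here is contradictory. Section 4.6.9 says what to do once hyperlipidaemia is found, no section forbids a lipid test, and 4.6.9 itself alerts investigators to the effect. Sections 4.4 and 7 oblige them to watch for adverse reactions, and a careful investigator would order lipids. All of this stands, and it is why the consequence can only be called possible. It does not close the gap, because those general duties name no lipid test and, for urine protein and thyroid function, the protocol does not rely on them alone.

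A second reply is that no magnitude is shown. That also stands. A range of 0% to 100% is no estimate, so high confidence attaches to the reading of the lists and not to any harm.

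Third, more testing has its own effects. Section 4.4, item (6) Others, delays and reduces dosing at grades 2–3 and stops it at grade 4, so newly detected lipid values could lead to dose delays or reductions. Section 4.6.9 is silent on anlotinib dosing, and the two provisions can apply together. How they should combine at grades 2–3 is a question for the clinical team. A reader might infer that lipid elevations ought to be exempt from the Others rule, but no section supports that.

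**Conclusion.** The omission is real and verifiable: a stated drug effect, a laboratory trigger for treatment, no lipid analyte in any of the four scheduled panels, and no test interval in 4.6.9. The treatment rule and the reported lipid adverse-event incidence therefore rest on unscheduled testing without a scheduled baseline. The extent is unknown.

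Three stronger readings are not supported. A reader might infer that lipid toxicity will be missed in some definite share of patients; the documents give nothing from which to compute one. A reader might infer that the trial's conclusion is at risk; the primary endpoint is disease control by RECIST 1.1, and neither it, nor the sample size, nor the 11-case rule uses lipid data. A reader might infer that lipids were singled out; lipase shows they were not.

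This is a minor point, worth acting on because the remedy is cheap. It does not rely on the cholesterol figure printed in 4.6.9, which may be a text-extraction error, or on Appendix III, which shows no lipid row in the text available.

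**What to change.** Add triglycerides and total cholesterol to the existing chemistry draws at screening (5.1), before each cycle or every two cycles (5.3), at the 30-day follow-up (5.4) and at early termination (5.5). Ask for fasting samples where possible. Dosing is before breakfast (4.3) and the 5.3 tests precede dosing, so this should be practical.

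The cost is two routine analytes on blood already taken, with no added visit or needle stick: at most 156 to 546 samples over the assumed durations if tested each cycle, or 117 to 312 if tested every two cycles. Other downsides are more low-grade laboratory adverse events, more use of statins (a class that 4.5.1.2 lists for caution) and possible dose delays or reductions under the Others rule in 4.4. The clinical team should be asked how that rule and 4.6.9 apply together; the answer is not part of this change.

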#### **4.6.10 Stomatitis**

Stomatitis is one of the common adverse reactions of VEGFR inhibitors. For patients with stomatitis, Houfengsan, Kangfuxin and mouthwash are recommended.

#### **4.6.11 Reversible posterior leukoencephalopathy syndrome (RPLS)**

Reversible posterior leukoencephalopathy syndrome (RPLS) has been reported in cancer patients treated with VEGFR inhibitors and can be fatal. RPLS is a neurological disorder that may be accompanied by headache, seizures, somnolence, confusion, blindness, other visual and neurological disturbances, and mild to severe hypertension. MRI is the best established diagnostic method for RPLS. No such events have been reported in anlotinib studies, and relevant symptoms and signs should be closely monitored during practice. Permanent discontinuation is recommended for patients with RPLS.

### **5. STUDY PROCEDURES**

Patients must read and sign the informed consent form (ICF) approved by the Ethics Committee (EC) prior to the study. The examinations for subjects and test procedures should be conducted according to the schedule of the clinical study, irrespective of the duration of drug discontinuation. Changes due to holidays, festivals and other administrative reasons are allowed within the time window of each examination.

#### **5.1 Screening**

The screening period begins with the signing of ICF and ends with the administration of the study drug or screening failure. Subjects must sign the ICF before undertaking the screening procedures specified in this study. Results from laboratory tests and radiological assessments required for routine clinical care prior to ICF signing may be used if they are within the specified time window.

Unless otherwise specified, the following procedures should be completed within 28 days prior to the administration of the study drug.

- Signing the informed consent form;
- Collection of demographics: Sex, date of birth, ethnicity, height, body weight;
- Tumor diagnosis: Primary tumor site, date of pathological diagnosis, pathological grade and metastatic site;
- History of tumor treatment
  - ✓ History of tumor surgery: Name of surgery, date of surgery, postoperative TNM stage, date of postoperative recurrence;
  - ✓ History of radiotherapy: Site of radiotherapy, dose, start and end dates;
  - ✓ History of neoadjuvant chemotherapy: Chemotherapy regimen, cycle, start and end time;
  - ✓ History of adjuvant chemotherapy: Chemotherapy regimen, cycle, start and end time;
  - ✓ Salvage therapy: Regimen, cycle, start and end time, best response, time to tumor progression, treatment change due to tumor progression;
  - ✓ History of comorbidities, past medications, and drug allergy;
  - ✓ Virology tests (within 14 days prior to the first dose): HbsAg (if positive, HBV-DNA test is required), HBsAb, HBeAg, HBeAb, HBcAb, HCV-Ab (if positive, HCV-RNA test is required), HIV-Ab, EBV-DNA;

The following procedures and a pregnancy test should be completed within 7 days and 72 hours prior to the administration of the study drug, respectively:

- ✓ ECOG score;
- ✓ Vital signs: Pulse, respiratory rate, body temperature, blood pressure;
- ✓ Comprehensive physical examination: General condition, head and face, skin, lymph nodes, neck, eyes, ENT, oral cavity, respiratory system, cardiovascular system, abdomen, reproductive-urinary system, musculoskeletal system, nervous system, mental status, and others;
- ✓ Blood routine: Red blood cell count, hemoglobin, platelet count, white blood cell count, neutrophil count, lymphocyte count;

- ✓ Urinalysis: White blood cell count, red blood cell count, urine protein. If urine protein is  $\geq 2+$ , a 24-hour urine protein test is required;
- ✓ Fecal occult blood;
- ✓ Clinical chemistry: ALT, AST, GGT, total bilirubin, direct bilirubin, AKP, blood urea nitrogen or urea (blood urea nitrogen is preferred), total protein, albumin, creatinine, blood glucose, lactate dehydrogenase,  $K^+$ ,  $Na^+$ ,  $Ca^{2+}$ ,  $Mg^{2+}$ ,  $Cl^-$ ;
- ✓ Thyroid function: TSH, FT3, FT4;
- ✓ Coagulation function: APTT, PT, FIB, INR;
- ✓ Echocardiogram: LVEF assessment is included. Tests as clinically indicated;
- ✓ 12-lead ECG: Additional necessary tests should be performed according to the judgment of the investigators in case of any abnormality;
- ✓ Pregnancy test: Serum or urine (applicable to women of childbearing age);
- ✓ Radiological examination: CT or MRI of the nasopharynx, neck, chest, upper and lower abdomen (including the pelvis). Brain MRI (if MRI is contraindicated, CT can be used instead) should be performed when brain metastasis is suspected and confirmed. A bone scan should only be performed when clinically indicated and must be performed within 42 days before the first dose. During the screening period, tumor assessment can be completed within 4 weeks before administration, and radiological results obtained before signing the ICF can be used for tumor assessment as long as they meet the RECIST 1.1;
- ✓ AEs: AEs are recorded from the signing of ICF.

## **5.2 Enrollment**

- **Confirmation of eligibility.**
- **Dosing.**

## **5.3 Treatment Period**

- The following assessments should be completed before each dose in each cycle. If the test is completed within 7 days before the first dose during the screening

period, it is not required prior to the first dose.

- ✓ ECOG score;
- ✓ Vital signs: Pulse, respiratory rate, body temperature, blood pressure;
- ✓ Physical examination: General conditions, head and face, skin, lymph nodes, neck, eyes, ENT, oral cavity, respiratory system, cardiovascular system, abdomen, reproductive-urinary system, musculoskeletal system, nervous system, mental status, and others;
- ✓ Blood routine: Complete blood count and differential count (white blood cells, red blood cells, lymphocytes, monocytes, neutrophils, basophils, eosinophils, hemoglobin), platelet count;
- ✓ Clinical chemistry: ALT, AST, GGT, total bilirubin, direct bilirubin, AKP, blood urea nitrogen or urea (blood urea nitrogen is preferred), total protein, albumin, creatinine, blood glucose, lactate dehydrogenase, K+, Na+, Ca2+, Mg2+, Cl;
- ✓ EBV-DNA test;
- ✓ Urinalysis: White blood cell count, red blood cell count, urine protein. If urine protein is  $\geq 2+$ , a 24-hour urine protein test is required;
- ✓ Routine stool test: White blood cells, red blood cells, occult blood;
- ✓ Coagulation function: Prothrombin time, activated partial thromboplastin time, thrombin time, fibrinogen, D-dimer, international normalized ratio;
- ✓ Thyroid function: TSH, FT3, FT4 (FT3 and FT4 can be replaced by T3 and T4 if they are not available);
- ✓ 12-lead electrocardiogram (12-Lead ECG): Additional necessary tests should be performed according to the judgment of the investigators in case of any abnormality;
- ✓ Concomitant medication: Concomitant medication should be recorded in detail;
- ✓ AEs: AEs should be recorded in detail;
- Radiological examination (completed before dosing every two cycles): CT or MRI of the nasopharynx, neck, chest, and abdomen (including the pelvis). An enhanced scan is preferred if not contraindicated. The radiological examination should be performed every 6 weeks. For bone metastases, a bone scan is

performed only if the response for other lesions is assessed as CR and it is necessary to confirm whether bone metastases have completely disappeared or there are clinical indications. Subjects who withdraw from the study for any reason should undergo radiological examination at the time of withdrawal if no such examination has been performed within 3 weeks. Conditions for radiological examination should be the same as those at baseline (including scan slice thickness and contrast agent). A time window of  $\pm 7$  days is permitted for radiological examination, and unscheduled radiological examination can be performed when PD is suspected (e.g., symptomatic deterioration). In addition to radiologically confirmed PD, subjects who discontinue study treatment for other reasons should also undergo radiological examination every 6 weeks until documented PD, initiation of new antitumor therapy, loss to follow-up, or death. The time of radiological examination will not be adjusted for the delayed dosing period.

## **5.4 Follow-up**

On-site follow-ups will be conducted 30 days after the last dose at the study site, and safety information (including AE outcome, new SAEs, and adverse events of special interest) will be collected by telephone follow-ups at 60 and 90 days after the last dose, with a time window of  $\pm 7$  days.

If a subject starts a new antitumor therapy within 30 days after the last dose, the follow-up should be completed before the new antitumor therapy.

- ✓ Blood routine: Red blood cell count, hemoglobin, platelet count, white blood cell count, neutrophil count, lymphocyte count;
- ✓ Clinical chemistry: ALT, AST, GGT, total bilirubin, direct bilirubin, AKP, blood urea nitrogen or urea (blood urea nitrogen is preferred), total protein, albumin, creatinine, blood glucose, lactate dehydrogenase, K+, Na+, Ca2+, Mg2+, Cl;
- ✓ Thyroid function: TSH, FT3, FT4;
- ✓ AEs: AEs should be recorded in detail;

Concomitant medication: Concomitant medications are recorded until 90 days after the last dose. Concomitant medications for study drug-related AEs are recorded until 30 days after the last dose.

Survival follow-up will be performed by telephone and other effective methods once a month from the last dose to determine if the subject has initiated new antitumor therapy subsequently. If so, the treatment regimen, as well as start and end time will be recorded and the survival follow-up form will be completed.

For subjects who withdraw from the study due to "non-PD" (such as intolerable AEs), tumor assessment is recommended to be performed according to the frequency of efficacy evaluation specified in this study (every 6 weeks  $\pm$  7 days) during the tumor progression follow-up until PD, death or initiation of new antitumor therapy. The follow-up information should be recorded in the CRF.

